**[name]**  
**Medical Student, Indiana University School of Medicine**

**Version 5.0 10-21-19**

## 1.0 Background

Indiana University Hospital is a large academic health center that performs a large number (~180) of cystectomies per year. Cystectomy is a urologic procedure that involves the radical removal of the bladder, with subsequent need for urinary tract reconstruction. The reconstruction requires harvesting of portions of the small and/or large bowel, and can be in the form of an ileal conduit, orthotopic bladder replacement, or continent urinary reservoir such as an "Indiana Pouch". The postoperative course usually spans on average a 7-day inpatient hospital stay, with the majority of the issues surrounding management of postoperative pain and subsequent ileus. Currently, there is no standard of pain control in cystectomy, though adjunctive mechanisms of analgesia are often utilized to decrease opioid usage. Opioid use has long been associated with postoperative ileus, nausea and vomiting, aspiration, prolonged hospital stay, and several other side effects. Postoperative pain may also decrease patient satisfaction while increasing length of hospital stay and hospital costs. Without a standard practice for postoperative pain control in cystectomy, our study aims to compare thoracic epidural versus rectus sheath block versus surgeon infiltration of local anesthesia for cystectomy. With studies indicating improvements in perioperative outcomes for all three techniques, we believe we should compare these three methods for possible incorporation of the best technique for our enhanced recovery after surgery (ERAS) protocol for cystectomy. This will be done by collection of post-operative pain scores (VAS) at both resting and with movement. The VAS (Visual Analog Scale) pain scores will be measured at 24, 48, 72 and 96 hours under an advanced recovery perioperative care pathway.

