## 2.0 Rational and Specific Aims

All of the pain control modalities in this study have been used as postoperative analgesia in prior studies. The specific aim of this study is to compare the difference between the pain control methods in achieving the following:

1. Decreased opioid requirements
2. Improved postoperative VAS (Visual Analog Scale) pain scores
3. Decreased opioid side effects (Nausea, sedation, ileus, respiratory depression)
4. Decreased hospital length of stay (LOS)

The primary endpoint of this study will be VAS (Visual Analog Scale) pain score at both resting and with movement. The VAS Visual Analog Scale) pain score will be measured at 24, 48, 72 and 96 hours under an advanced recovery perioperative care pathway.

The secondary endpoint includes intravenous opioid consumption, opioid side effects (nausea, sedation, ileus, respiratory depression), and LOS. Hospital length of stay (LOS) will be collected via EMR of the admission and discharge date to calculate the LOS. The IV and PO opioid doses will be quantified at 1, 24, 48, 72, and 96 hours. All the opioid consumption (both PO and IV) will be converted to PO morphine equivalent for analysis. We will also measure postoperative nausea and sedation scores at 1, 24, 48, 72, and 96 hours. Nausea will be measured on a 4-point scale: none, mild, moderate or severe. This is collected as patient reported as well as per nursing documentation. Sedation score is also reported on a 4-point scale: awake/alert, quietly awake, asleep/arousable or deep sleep. This is collected as an observation by nurse coordinator/staff. We will access patient's satisfaction at 24, 48, 72 and 96 hours. This will be measured on a 5-point scale; very unsatisfied, unsatisfied, neutral, satisfied and very satisfied. We will also measure time to first flatus, postoperative creatinine, incidence of hypotension (defined as BP decrease of more than 20%), incidence of respiratory depression, and ambulation activity.

Ambulation is defined as anytime out of bed (up in chair, to bathroom and walking in hall with PT/nurse) activity will also be recorded daily. It will be recorded as yes/no.

---

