## **7.0 Statistical consideration**

Primary outcome: VAS score with movement at 48 and 72 hours

Primary Research Hypothesis: Thoracic epidural will provide lower postoperative pain scores compared to each of the other three methods used for cystectomy as measured by VAS scores at 24, 48, 72, and 96 hours under an enhanced recovery perioperative care pathway.

Secondary outcomes: Narcotic usage after 1, 24, 48, 72, and 96 hours. Pain scores using VAS at rest and on knee flexion at 1, 24, 48, 72, and 96 hours. Nausea scores at 1, 24, 48, 72, and 96 hours. Sedation scores at 1, 24, 48, 72, and 96 hours. Time to first flatus, postoperative creatinine, hospital length of stay (hospital length of stay (LOS) will be collected via EMR of the admission and discharge date to calculate the LOS), ileus, hypotension (defined as BP decrease of more than 20%), and ambulation/anytime out of bed (up in chair, to bathroom and walking in hall with PT/nurse) activity will also be recorded daily. It will be recorded as yes/no.

If the patient is discharged within 96 hours, every effort will be made to obtain data points, but we will not consider these data point deviations since our 96-hour data point will not change the integrity of the study.

Secondary Research Hypotheses: Thoracic epidural will show improved patient satisfaction scores and decreased nausea and sedation scores compared to each of the other three treatments.

Statistical analysis will be performed using a standard statistical program (SAS or SPSS). All data will be summarized (means, standard deviations, standard errors, and ranges for continuous variables; frequencies and percentages for categorical variables) by group. Demographic data will be compared between the four groups using ANOVA or chi-square tests as appropriate. The primary outcome, VAS ( Visual Analog Scale) at 48 and 72 hours, will be compared between the

groups using repeated measures ANOVA; the model will include fixed effects for group, time, and the group by time interaction and random effects to allow correlations between the two times and different variances for the two times.

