Pain and satisfaction scores and opioid usage over time will be analyzed using repeated measures ANOVA. Nausea and sedation scores will be compared between groups at each time point using Mantel-Haenszel chi-square tests for ordered categorical data. Time to first flatus, postoperative creatinine, and LOS will be compared between the groups using one-way ANOVA. The binary outcomes of incidence of ileus, hypotension (defined as BP decrease of more than 20%), and incidence of respiratory depression will be analyzed using logistic regression. Distributions of the continuous variables will be examined, and a transformation of the data (e.g. natural logarithm) or nonparametric tests will be used as necessary. A 5% significance level will be used for all comparisons.

Based on prior studies, the coefficient of variation for the VAS ( Visual Analog Scale) score at 48 and 72 hours is estimated to be 0.70. With a sample size of 40 per group the study will have 80% power to detect a ratio of means of 1.5 for VAS score between any two of the four treatment groups, assuming two-sided tests each conducted at a 5% significance level.

All patients will receive a phone survey approximately 6 months after surgery to assess for pain, quality of life, and satisfaction of hospital stay. Quality of life is measured by how their pain interferes with their general activity, mood, walking ability, normal work, relations with other people, sleep and enjoyment of life. If after four attempts to contact the patient are unsuccessful, the survey will not be completed; this will not be considered a deviation as the survey is not critical to the overall data collection.

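### Nine secondary outcomes besides nausea and sedation are each tested at an unadjusted 5%, with no testing order, no link to the primary result and no exploratory label

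*Combined protocol and SAP*

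**What the plan says.** Section 7.0 of the combined protocol and SAP names movement VAS at 48 and 72 hours as the primary outcome and lists the secondary outcomes separately. It then assigns tests:

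- Repeated measures ANOVA for pain scores, satisfaction and opioid use.
- One-way ANOVA for three more: "Time to first flatus, postoperative creatinine, and LOS will be compared between the groups using one-way ANOVA".
- Logistic regression for ileus, hypotension and respiratory depression.
- Mantel-Haenszel tests at each time point for nausea and sedation, which are left out of the count here.

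The section closes the list with "A 5% significance level will be used for all comparisons". The power statement uses the same per-test level: "assuming two-sided tests each conducted at a 5% significance level".

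The secondary hypothesis reads "Thoracic epidural will show improved patient satisfaction scores and decreased nausea and sedation scores compared to each of the other three treatments". Section 2.0 introduces its four aims with "The specific aim of this study is to compare the difference between the pain control methods in achieving the following"; they are opioid requirements, VAS, opioid side effects and LOS. Directly afterwards it makes VAS the primary endpoint and the other three secondary. Section 1.0 gives the purpose as "possible incorporation of the best technique for our enhanced recovery after surgery (ERAS) protocol for cystectomy".

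**The concern.** The division into primary and secondary outcomes has no stated consequence for inference. A p-value below 0.05 on LOS or time to flatus carries the same declared level as one on movement VAS, and it may be reported whether or not movement VAS differs between the arms. Several of these outcomes are tied to the study's aims (opioid use, side effects, LOS) or to a stated hypothesis (satisfaction), and the results are meant to inform the choice of technique for the recovery pathway. With many tests at full level and no rule for weighing them, the plan gives a reader no agreed way to separate a chance difference from an established one.

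**Working it through.** **1. The plan's own figure.** Section 7.0 states "80% power to detect a ratio of means of 1.5 for VAS score between any two of the four treatment groups", with 40 per group, on the basis that "the coefficient of variation for the VAS ( Visual Analog Scale) score at 48 and 72 hours is estimated to be 0.70".

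- Log-scale SD = √ln(1 + 0.70²) = √ln 1.49 = 0.6315.
- Standard error of a two-group difference = 0.6315 × √(2/40) = 0.1412.
- ln 1.5 / 0.1412 = 0.4055 / 0.1412 = 2.871.
- Power = Φ(2.871 − 1.960) = Φ(0.911) = 81.9%; with a noncentral t on 78 df, 80.9%.

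The stated 80% is reproduced using 5% for one pairwise test. The plan's 5% is therefore a per-test level, and no familywise rate is stated anywhere.

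**2. The count.** Pain scores, satisfaction and opioid use (3), flatus, creatinine and LOS (3), ileus, hypotension and respiratory depression (3) make nine. Pain scores count once. Ambulation is listed as an outcome but has no stated test, so it is not counted.

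**3. The tests as written: one four-group test per outcome.** With no true difference and independent outcomes, the chance of at least one false result is 1 − 0.95⁹ = 1 − 0.630 = 37.0%. Outcomes such as opioid use, ileus, flatus and LOS are unlikely to be independent. The documents give no correlations, so a range is assumed. Two separate simulations (40,000 trials per setting, four equal arms, all nine outcomes treated as normal, exchangeable correlation, 3-df test at 5%) gave:

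| Assumed correlation | At least one false four-group result |
|---|---|
| 0 | 36.7% and 37.0% |
| 0.2 | 35.0% and 35.4% |
| 0.5 | 28.4% and 27.8% |
| 0.8 | 17.3% and 17.5% |

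**4. If epidural-versus-each contrasts were also run unadjusted.** The chance of at least one false result among three contrasts sharing the epidural arm is 12.5% per outcome. Over nine independent outcomes it is 1 − 0.875⁹ = 70%; simulation gives 56% at correlation 0.5 and 37% at 0.8. The expected number of false positives is 27 × 0.05 = 1.35. This family is conditional: among the nine, only satisfaction has that hypothesis in the plan.

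**5. Sensitivity to the normal approximation.** Three outcomes are binary with 40 per arm, and the documents give neither event rates nor the form of the logistic test. At an assumed 5% event rate, a Wald four-group test rejects in about 0.1% of trials under the null and a likelihood-ratio test in about 7%. Under independence, the 37% then becomes 1 − 0.95⁶ × 0.999³ = 27% or 1 − 0.95⁶ × 0.93³ = 41%.

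**6. One arm beating all three others.** Under the null this happens in 0.65% of trials per outcome, so over nine independent outcomes 1 − 0.9935⁹ = 6%.

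**The case against.** The strongest reply is that the plan does separate primary from secondary outcomes, powers the trial on VAS alone and promises only a per-comparison 5%. On that view many readers would already treat the secondary p-values as supportive, and how strictly to control them in a single-centre comparison is partly a matter of preference. Much of this stands. The split exists, no promised familywise rate has been broken, and five of the nine (LOS, flatus, creatinine, ileus, hypotension) have no stated superiority hypothesis. What it does not answer is that the plan never tells the reader to treat these results as supportive; its only rule gives every comparison the same level.

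A reader might go further in three ways, and the documents support none of them:

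- **That a false finding is likely.** The tests as written reach about 37% at most under the normal model (about 41% under the least favourable binary assumption above). Figures above one half need pairwise contrasts that the plan does not specify for eight of the nine outcomes. The any-two-groups wording belongs to the VAS power statement.
- **That a false best technique would be declared.** A significant four-group test names no best arm, and one arm beating all three others by chance on some outcome occurs in only about 6% of trials. Creatinine, hypotension and respiratory depression also read more as safety outcomes than as grounds for choosing a technique.
- **That the secondary outcomes stand level with VAS.** Section 2.0 lists them together as aims, then separates them as endpoints.

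**Conclusion.** The point holds in a limited form. Nine secondary outcomes are tested at an unadjusted 5% with no order, no dependence on the primary result and no exploratory label. The central figure is about a 28% chance of at least one false between-group difference (17% to 37%). It rests on a global null, equal arms, the normal approximation and an assumed correlation of 0.5 (range 0.8 to 0). The 37% to 70% range applies only if the unadjusted epidural contrasts are added. The primary analysis and its power are untouched, so the issue is what the secondary results may be used to claim. It should be corrected, and it does not threaten the trial's main result.

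**What to change.** In section 7.0, replace the sentence that sets one level for all comparisons with:

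> The 5% level for confirmatory claims applies to the primary outcome. All secondary outcomes, including nausea, sedation and satisfaction, are exploratory: they are reported as estimates with 95% confidence intervals, p-values are nominal, and they do not on their own support a claim that one technique is superior.

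If the sponsor wants a confirmatory claim on a secondary outcome such as satisfaction, it should name that outcome and apply Holm adjustment across its tests, fixed before data are analysed.

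A fixed sequence of secondary outcomes behind the primary hypothesis is possible but less attractive. That hypothesis requires epidural to beat each of three arms. At the planned ratio of 1.5 and one time point, the Holm-adjusted version fails in about 37% to 39% of trials even when the planned effect is real, which would close off all secondary testing.

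The recommended change needs no patients and no new data, and it leaves primary power at about 81% to 82%. The downside is that a nominal p<0.05 on a secondary outcome can no longer be reported as a confirmed difference.

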## **8.0 Privacy**

All study papers containing patient identifiers will be kept in each subjects' confidential study file accessible to only the research team. All records will be kept in a locked room in a locked cabinet that only authorized staff enters. Collected data from each enrolled participant will be recorded on Redcap, which is a secure web-based data collection tool. Three years after completion of the study, all electronic information and paperwork containing patient identifiers will be deleted or shredded.

## **9.0 Follow-up/record retention**

The study will start in August of 2019 and will end when a sample size of 160 subjects is achieved. Since Indiana University Hospital performs a large number (~180) of cystectomies per year, the estimated time frame to enroll 160 study subjects is 24 months. After 160 subjects have been enrolled, the study will be stopped and the data collected will be analyzed using statistical methods.

Three years after completion of the study, all study papers with patient identifiers will be shredded and only data without any patient identifiers will be retained by the research team for an indefinite time.

Butterworth Iv, John F., David C. Mackey, and John D. Wasnick. "Spinal, Epidural, &Amp; Caudal Blocks." In *Morgan &Amp; Mikhail's Clinical Anesthesiology, 6e*. New York, NY: McGraw-Hill Education, 2018.

de Boer, H. D., O. Detriché, and P. Forget. "Opioid-Related Side Effects: Postoperative Ileus, Urinary Retention, Nausea and Vomiting, and Shivering. A Review of the Literature." [In eng]. *Best Pract Res Clin Anaesthesiol* 31, no. 4 (Dec 2017): 499-504.

Guo, Q., R. Li, L. Wang, D. Zhang, and Y. Ma. "Transversus Abdominis Plane Block Versus Local Anaesthetic Wound Infiltration for Postoperative Analgesia: A Systematic Review and Meta-Analysis." [In eng]. *Int J Clin Exp Med* 8, no. 10 (2015): 17343-52.

Hou, X., Z. Luo, H. Wang, Y. Zhan, L. Yang, and L. Li. "[Effect of Adductor Canal Block Combined with Local Infiltration Anesthesia on Rehabilitation of Primary Total Knee Arthroplasty]." [In chi]. *Zhongguo Xiu Fu Chong Jian Wai Ke Za Zhi* 32, no. 8 (Aug 1 2018): 1006-11.

Kalogera, E., J. N. Bakkum-Gamez, A. L. Weaver, J. P. Moriarty, B. J. Borah, C. L. Langstraat, C. J. Jankowski, et al. "Abdominal Incision Injection of Liposomal Bupivacaine and Opioid Use after Laparotomy for Gynecologic Malignancies." [In eng]. *Obstet Gynecol* 128, no. 5 (Nov 2016): 1009-17.

Ladjevic, N., I. Likic-Ladjevic, Z. Dzamic, M. Acimovic, D. Dragicevic, and O. Durutovic. "Combined General and Epidural Anaesthesia Versus General Anaesthesia for Radical Cystectomy." [In eng]. *Acta Chir Iugosl* 54, no. 4 (2007): 89-91.

Mazul-Sunko, B., I. Gilja, M. Jelisavac, I. Kozul, D. Troha, N. Osmancevic, A. El-Saleh, et al. "Thoracic Epidural Analgesia for Radical Cystectomy Improves Bowel Function Even in Traditional Perioperative Care: A Retrospective Study in Eighty-Five Patients." [In eng]. *Acta Clin Croat* 53, no. 3 (Sep 2014): 319-25.

